### 11.6.2. Handling of Missing Data

Element	Reporting Detail
General	
 
Missing data occurs when any requested data is not provided, leading to blank fields on the collection instrument: 
 
These data will be indicated by the use of a “blank” in participant listing displays. Unless all data for a specific visit are missing in which case the data is excluded from the table.
 
Answers such as “Not applicable” and “Not evaluable” are not considered to be missing data and should be displayed as such.
 
 
 

Outliers	
 
Any participants excluded from the summaries and/or statistical analyses will be documented along with the reason for exclusion in the clinical study report.
 

CCI	
 
Subjects who were injected that have missing CCI data may have it imputed with their last observation carried forward (LOCF)
 

#### 11.6.2.1. Handling of Missing and Partial Dates

Element	Reporting Detail		
General	
 
Partial dates will be displayed as captured in participant listing displays.
 
Where necessary, partial dates may be imputed for specific analysis purposes as outlined below.
 
Imputed partial dates will not be used to derive study day, time to onset or duration (e.g., time to onset or duration of AEs), or elapsed time variables (e.g., time since diagnosis).
 
		
Adverse Events	
 
Imputations in the AEs dataset are used for slotting events to the appropriate study time periods and for sorting in data listings.
 
Partial dates for AE recorded in the eCRF will be imputed using the following conventions: 
 
 Missing start day	 
 
If study treatment start date is missing (i.e. participant did not start study treatment), then set start date = 1st of month.
 
Else if study treatment start date is not missing: 
 
If month and year of start date = month and year of study treatment start date then 
 
If stop date contains a full date and stop date is earlier than study treatment start date then set start date= 1st of month.
 
 
 
 
 
 	
 
 
 
	Missing start day	
 
If study treatment start date is missing (i.e. participant did not start study treatment), then set start date = 1st of month.
 
Else if study treatment start date is not missing: 
 
If month and year of start date = month and year of study treatment start date then 
 
If stop date contains a full date and stop date is earlier than study treatment start date then set start date= 1st of month.
 
 
 
 
 

Missing start day	
 
If study treatment start date is missing (i.e. participant did not start study treatment), then set start date = 1st of month.
 
Else if study treatment start date is not missing: 
 
If month and year of start date = month and year of study treatment start date then 
 
If stop date contains a full date and stop date is earlier than study treatment start date then set start date= 1st of month.
 
 
 
 
 
		

Element	Reporting Detail	
		
 
▪ Else set start date = study treatment start date.
 
○ Else set start date = 1st of month.
 

	Missing start day and month	
 
• If study treatment start date is missing (i.e. participant did not start study treatment), then set start date = January 1.
 
• Else if study treatment start date is not missing: 
 
○ If year of start date = year of study treatment start date then 
 
▪ If stop date contains a full date and stop date is earlier than study treatment start date then set start date = January 1.
 
▪ Else set start date = study treatment start date.
 
○ Else set start date = January 1.
 
 
 
 
 

	Missing stop day	Last day of the month will be used.
	Missing stop day and month	No Imputation
	Completely missing start/end date	No imputation
	
 
• Completely missing start or end dates will remain missing, with no imputation applied.
 
	
Concomitant Medications	
 
• Partial dates for any concomitant medications recorded in the eCRF will be imputed using the following convention:
 
	
	Missing start day	
 
• If study treatment start date is missing (i.e. participant did not start study treatment), then set start date = 1st of month.
 
• Else if study treatment start date is not missing: 
 
○ If month and year of start date = month and year of study treatment start date then 
 
▪ If stop date contains a full date and stop date is earlier than study treatment start date then set start date= 1st of month.
 
▪ Else set start date = study treatment start date.
 
○ Else set start date = 1st of month.
 
 
 
 
 

	Missing start day and month	
 
• If study treatment start date is missing (i.e. participant did not start study treatment), then set start date = January 1.
 
• Else if study treatment start date is not missing: 
 
○ If year of start date = year of study treatment start date then 
 
▪ If stop date contains a full date and stop date is earlier than study treatment start date then set start date = January 1.
 
▪ Else set start date = study treatment start date.
 
• Else set start date = January 1.
 
 
 
 
 

	Missing end day	A '28/29/30/31' will be used for the day (dependent on the month and year)
	Missing end day and month	A '31' will be used for the day and 'Dec' will be used for the month.
	Completely missing start/end date	No imputation
	
 
• The recorded partial date will be displayed in listings.
 
	

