## **6. STUDY INTERVENTION**

Study intervention is defined as any investigational intervention(s), marketed product(s), placebo, or medical device(s) intended to be administered to a study participant according to the study protocol.

Investigational product (IP) in this protocol refers to the investigational study drugs Oral CAB, CAB LA, Oral RPV, and RPV LA. CAB and RPV products will be supplied by GlaxoSmithKline/ViiV Healthcare and Janssen Pharmaceuticals, respectively.

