### **8.2.1. Time Period and Frequency for Collecting AE and SAE Information**

- All SAEs will be collected from the start of intervention until the follow-up Week 52 visit at the time points specified in the SoA (Section [1.3](#)). However, any SAEs assessed as related to study participation (e.g., study intervention, protocol-mandated procedures, invasive tests, or change in existing therapy) or related to a GSK/ViiV product will be recorded from the time a participant consents to participate in the study.
- All AEs will be collected from the start of intervention until the follow-up Week 52 visit at the time points specified in the SoA (Section [1.3](#)).

- Medical occurrences that begin before the start of study intervention but after obtaining informed consent will be recorded on the Medical History/Current Medical Conditions section of the CRF not the AE section.
- All SAEs will be recorded and reported to the sponsor or designee immediately and under no circumstance should this exceed 24 hours, as indicated in [Appendix 3](#). The investigator will submit any updated SAE data to the sponsor within 24 hours of it being available.
- Investigators are not obligated to actively seek AEs or SAEs after the conclusion of the study participation. However, if the investigator learns of any SAE, including a death, at any time after a participant has been discharged from the study, and he/she considers the event to be reasonably related to the study intervention or study participation, the investigator must promptly notify the sponsor.

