## 11.8. Appendix 8: Permissible Procedures during the COVID-19 Pandemic

The COVID-19 pandemic presents significant logistical challenges for many clinical sites around the world, with variable restrictions being placed on site resources and operations, and on an individual participant's ability to attend clinic visits. Based on these challenges, it may be necessary to adopt additional measures and procedures to protect participant safety, and to allow flexibility to allow conduct of the study.

Permissible changes to procedures during the COVID-19 pandemic if deemed necessary by the investigator are outlined below. The investigator should discuss with the medical monitor the rationale if any of these changes are required for a participant. For further details refer to the Study Reference Manual (SRM).

- Participants previously deemed eligible during the screening period unable to attend within the allowable screening window due to COVID-19 may be rescreened.
- Oral CAB dosing Days 1 to 28. All doses except Day 1 and Day 14 may be administered at home if participants are unable to attend due to COVID-19.
- AE assessments during the oral lead in may be conducted by telephone at home if participants are unable to attend due to COVID-19.
- Duration of admission to the clinic may be extended if deemed necessary by the investigator due to the COVID-19 pandemic.
- The 10 to 14-day washout period after the oral lead in may be extended if deemed necessary by the investigator due to the COVID-19 pandemic.

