## 5. CONSIDERATIONS FOR DATA ANALYSES AND DATA HANDLING CONVENTIONS

### 5.1. Treatment and Other Sub-Group Descriptions for Data Displays

Data display treatment descriptors with actual treatment dose will be defined as displayed in [Table 5](#). Safety events in the washout phase will be counted with events in the Oral lead-in phase. Safety events in the Follow-up phase will be counted separately from the Injection phase.

**Table 5** Study Treatment

Phase	Analysis	Treatment Group Descriptions			
		Code	Treatment Description	Treatment Description-Footnote	Column Header
Oral Lead-in	PK	A	Oral CAB 30mg tablet once daily x 4 weeks lead-in	Oral CAB 30mg=Cabotegravir 30mg PO 4 weeks lead-in	Oral CAB 30mg
		B	Oral RPV 25mg tablet once daily x 4 weeks lead-in	Oral RPV 25mg=Rilpivirine 25mg PO 4 weeks lead-in.	Oral RPV 25mg
	Safety	AB	Oral CAB 30mg + RPV 25mg tablets once daily x 4 weeks lead-in	Oral CAB 30mg + Oral RPV 25mg =Cabotegravir 30mg + Rilpivirine 25mg PO 4 weeks lead-in	Oral CAB 30mg + Oral RPV 25mg
	PK, Safety (ISRs), HO	C	Single 600mg CAB LA IM dose	IM CAB 600mg=Cabotegravir IM 600mg single dose.	IM CAB 600mg – Injection Phase; IM CAB 600mg – Follow-up Phase
		D	Single 900mg RPV LA IM dose	IM RPV 900mg=Rilpivirine IM 900mg single dose.	IM RPV 900mg – Injection Phase; IM RPV 900mg – Follow-up Phase
	Safety	CD	Single 600mg CAB + single 900mg RPV LA IM dose	IM CAB 600mg + IM RPV 900mg = Cabotegravir IM 600mg + Rilpivirine IM 900mg single dose.	IM CAB 600mg + IM RPV 900mg – Injection Phase; IM CAB 600mg + IM RPV 900mg – Follow-up Phase

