**Table 3 Assignment of Study Phases**

For All Events or Assessments	
Study Period	Date range
Screen	If actual “Time of Day” for the assessment/event is collected: Start Date and Time < OLI Treatment Start Date & Time
	If actual “Time of Day” for the assessment/event is not collected:
	Start Date < OLI Treatment Start Date
OLI Phase	If actual “Time of Day” for the assessment/event is collected: For participants continuing into Injection Phase: OLI Treatment Start Date & Time ≤ Start Date & Time < Date & Time of CAB + RPV Injection
	For participants not continuing into Injection Phase: OLI Treatment Start Date & Time ≤ Start Date & Time
	If actual “Time of Day” for the assessment/event is not collected:
	For participants continuing into Injection Phase: OLI Treatment Start Date ≤ Start Date < Date of CAB + RPV Injection
	For participants not continuing into Injection Phase: OLI Treatment Start Date ≤ Start Date
Injection Phase	If actual “Time of Day” for the assessment/event is collected: Date & Time of CAB + RPV Injection ≤ Start Date & Time and Start Date ≤ Date of Nominal Follow-up Week 4
	If actual “Time of Day” for the assessment/event is not collected:
	Date of CAB + RPV Injection ≤ Start Date ≤ Date of Nominal Follow-up Week 4 Visit
Follow-up Phase	Date of Nominal Follow-up Week 4 Visit < Start Date

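### Partial AE start dates are imputed against a single undefined treatment start date, with no rule at the injection or Week 4 boundaries, so some AEs with a missing start day are slotted to the wrong phase (minor)

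*SAP*

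**What the plan says.** SAP 11.6.2.1 states the purpose of the imputation: "Imputations in the AEs dataset are used for slotting events to the appropriate study time periods". For a missing start day it tests one date. If the AE's month and year match those of the study treatment start date, the AE takes that date, unless a full stop date is earlier. For every other month the instruction is "Else set start date = 1st of month", and that branch tests no stop date. The rule for a missing day and month uses the same single anchor; it is not sized here.

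The anchor is not defined. Its gloss reads "If study treatment start date is missing (i.e. participant did not start study treatment), then set start date = 1st of month". Protocol 6 counts the oral tablets as study drug: "Investigational product (IP) in this protocol refers to the investigational study drugs Oral CAB, CAB LA, Oral RPV, and RPV LA". The phase-assignment table in SAP 11.3.1 makes separate provision under "For participants not continuing into Injection Phase", so a participant can start treatment and never be injected. These places point to the first oral dose. However, the concomitant-medication table in SAP 11.3.1 names separate oral lead-in (OLI) and Injection Phase treatment start dates, and the Study Day rule in SAP 11.5.1 counts from an Intervention Phase start date.

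The phase-assignment table cuts AEs at three dates: first oral dose, injection and the nominal Week 4 visit. SAP 5.1 counts washout events with OLI and adds: "Safety events in the Follow-up phase will be counted separately from the Injection phase".

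**The concern.** The imputation serves to choose a phase, yet it looks at only one of the three dates that separate phases. Under the oral reading, any missing-day AE in the injection month becomes the 1st, which precedes the injection unless injection was on the 1st. An ISR shows the fault plainly: it cannot precede the injection, but would be counted under oral lead-in.

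At stake are the AE displays by phase: Tables 3.2, 3.4-3.13 (ISRs are excluded from 3.13 by title), 3.15-3.17, Figure 3.38, and the Phase column in Listings 9, 10, 11, 13 and 14. With about 15 injected participants, one misplaced AE shifts an injection-phase incidence by at most 1/15 = 6.7 percentage points, and only if that participant has no other AE in the row.

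**Working it through.** The plan gives no figure to reproduce. The check applies its two rules to every possible onset day.

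**Inputs**
- Oral dosing 28 days, washout 10-14 days (Protocol 4.1). Injection is then 37-41 days after the first oral dose if washout runs from the last dose, or 38-42 if 10-14 clear days follow it. Gaps of 37-42 days are used (mean 39.5).
- Week 4 visit on Injection Day 28 (SAP 11.2.1, Table 9).
- AE period: "All AEs will be collected from the start of intervention until the follow-up Week 52 visit" (Protocol 8.2.1), taken as Injection Day 364. Days per schedule: 39.5 + 28 + 336 = 403.5.
- Assumptions: 365 start dates equally likely, onset days equally weighted, month and year known, day missing.

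**Step 1: can the oral-start branch reach the injection month?** A gap of at least 37 days exceeds any month, so no: 0 of 365 × 6 = 2,190 schedules. The 1st-of-month branch always governs there.

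**Step 2: injection boundary, oral reading.** For injection on day k > 1 of a month of L days, min(28, L − k + 1) injection-phase days become the 1st and go to OLI; for k = 1, none. Sums over k:
- L = 31: 28 + 28 + (28 + … + 1) = 462
- L = 30: 28 + (28 + … + 1) = 434
- L = 28: 27 + … + 1 = 378

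(7 × 462 + 4 × 434 + 378)/365 = 5,348/365 = 14.65 days; 14.65/28 = **52.3%**. For onset on Injection Days 1-7 alone, enumeration gives 86.8%.

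**Step 3: Week 4 boundary, either reading.** For a visit on day v, the L − v later days of that month leave Follow-up. Sums are 465, 435 and 378. (7 × 465 + 4 × 435 + 378)/365 = 5,373/365 = 14.72 days; 14.72/336 = **4.4%**. Under the oral reading, 14.65 of these go to Injection and 0.07 to OLI.

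**Step 4: injection-date reading.** The k − 1 pre-injection days of the injection month now take the injection date: again 5,373/365 = 14.72 days move from OLI into Injection. In the first-oral-dose month, AEs become the 1st, so 14.72 oral-phase days fall in Screening. The fault changes place.

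**Step 5: would imputing the injection date for all AEs help?** Days misplaced per schedule, keeping the oral anchor:

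| Rule | OLI | Injection | Follow-up | Total | Correct |
|---|---|---|---|---|---|
| Plan, oral reading | 0 | 14.65 | 14.72 | 29.37 | 92.72% |
| Plus injection date for all AEs | 14.72 | 0 | 14.72 | 29.44 | 92.70% |

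It exchanges one error for another.

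**Step 6: how often is the phase in doubt?** By enumeration, 57.36 of 403.5 onset days (14.2%) lie in a month holding more than one on-study phase, about 1.9 such months per participant. Elsewhere the month fixes the phase.

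**Longer washout.** Protocol Appendix 8 allows this: "The 10 to 14-day washout period after the oral lead in may be extended". Gaps of 49, 56 and 70 days give the same 52.3% and 4.4%.

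**Example (assumed dates).** First oral dose 2 November 2020, injection 11 December, Week 4 visit 7 January 2021. An AE on 12 December with the day missing becomes 1 December (OLI). One on 12 January becomes 1 January (Injection).

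**The case against.** The strongest objection is that the 52.3% rests on a reading. The term is undefined and the SAP names other start dates elsewhere. Under an injection-date anchor the injection-to-OLI error disappears. This stands, and it limits confidence; but Steps 3 and 4 show that no reading makes the rule correct.

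Second, the error rate is highest where a missing day is least likely. AE and ISR assessments fall on Days 2, 4, 5, 7/8, 10, 15, 17, 22 and 28, so gaps are at most 6 days. The diary display in SAP 11.9.11 (HO_03) also dates injection-area symptoms by side. Follow-up visits are 4-16 weeks apart, where partial dates are more plausible, but there the share is 4.4%. This stands too: the number of affected AEs could be zero.

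Third, routine data checking (Protocol 11.1.6) may recover some dates, and this SAP is a critical-components version whose displays are still to be confirmed. Neither supplies a rule at these boundaries.

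A reader might infer that about half of injection-phase AEs will be misreported. The documents do not support that: the figure is conditional on a missing day, and no count of partial dates is given. Nor does a known stop date protect an AE in the injection month, because the governing branch never tests it.

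**Conclusion.** The concern holds as a minor defect, with medium confidence. The rule uses one undefined anchor and ignores two of the three phase boundaries. Given a missing start day and equally weighted onset days, 52.3% of injection-phase days go to OLI under the oral-dose reading, and 4.4% of follow-up days move earlier under either reading.

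It would be wrong to conclude that the safety results as a whole are unreliable. Under the oral-dose reading, Overall columns, treatment-emergent status, displayed dates, study day and duration are unaffected. Only an injection-date reading could push oral-phase AEs into Screening, which SAP 11.3.2 does not class as emergent; that is a further reason to name the anchor. ISR Tables 3.20-3.22 are split by side (SAP 7.3). The safety summaries are descriptive, and the primary PK endpoints are not involved.

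**What to change.** 1. For any AE whose partial start date falls in a month holding more than one phase, flag it, ask the site before database freeze whether onset was before or after the injection or the Week 4 visit, and slot by the answer.
2. Never slot an ISR before the injection. With a missing day in the injection month, use the dated diary where available; otherwise impute the injection date.
3. Name the anchor as the first oral dose.
4. If the site cannot answer for an AE that is not an ISR, keep the plan's imputed phase and the flag.

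Do not impute the injection date for all AEs: that does not raise accuracy. The cost is a few sentences in the SAP, a few lines of code and a few site queries among about 15 injected participants. Where the site cannot answer, the phase of a non-ISR AE stays uncertain, but visibly so.

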## 11.3. Appendix 3: Study Phases and Treatment Emergent Adverse Events

### 11.3.1. Study Phases

All assessments and events (including those collected as planned, early withdrawal and unscheduled visits) will be classified in study phases according to [Table 3](#).

Assessments/events are assigned to study phases sequentially, starting from the top of each table.

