**NOTES:**

- If concomitant medication time is missing, the medication will be assumed to be taken predose, prior to that day's treatment dosing.
- Please refer to Appendix 6: Reporting Standards for Missing Data. for handling of missing and partial dates for concomitant medication. Use the rules in this table if concomitant medication date is completely missing.

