**11.3.2. Treatment Emergent Flag for Adverse Events**

Flag	Definition
Treatment Emergent	
 
• AEs will be considered emergent in the OLI, Injection and Follow-up Phases according to the classification defined in Table 3. AEs that occur in the Follow-up Phase will be considered Treatment Emergent.
 

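### An adverse event with no start date at all is placed in Screening or in no phase, so it is never counted as treatment-emergent, although AE-form records are presumptively post-dose

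*SAP*

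**What the plan says.** **Missing AE dates (SAP 11.6.2.1).** The plan explains why AE dates are imputed: "Imputations in the AEs dataset are used for slotting events to the appropriate study time periods and for sorting in data listings". Partial dates get a rule. If the known month and year, or the known year alone, match those of treatment start, the start is set to the treatment start date, unless a full stop date is earlier. If nothing is known: "Completely missing start or end dates will remain missing, with no imputation applied".

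**Phase assignment (SAP 11.3.1).** "Assessments/events are assigned to study phases sequentially, starting from the top of each table". Where no time of day is collected, the first row (Screen) asks whether "Start Date < OLI Treatment Start Date". The last row (Follow-up) asks whether "Date of Nominal Follow-up Week 4 Visit < Start Date". The rows between are also start-date inequalities. No row or note covers an AE with no start date. The neighbouring table for concomitant medication does at least name the case: "Use the rules in this table if concomitant medication date is completely missing".

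**Treatment-emergent flag (SAP 11.3.2).** "AEs will be considered emergent in the OLI, Injection and Follow-up Phases according to the classification defined in" that phase table. Nothing else enters the flag.

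**What the AE form holds (Protocol 8.2.1).** AEs are collected from the start of intervention to Week 52. For anything earlier, the rule is: "Medical occurrences that begin before the start of study intervention but after obtaining informed consent will be recorded on the Medical History/Current Medical Conditions". Such occurrences therefore stay off the AE form. The exception is SAEs related to study participation or to a sponsor product, which are recorded from consent.

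**The concern.** The less that is known about an AE's onset, the more cautious a safety summary should be in keeping it. Here the default reverses. An AE with only a year that matches treatment start is counted as treatment-emergent; the same AE with no date is not. Protocol 8.2.1 gives good reason to presume that an undated AE-form record began on or after first dose, so the more natural default is the opposite of the one the SAP produces.

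At stake are the treatment-emergent count in Table 3.2, the treatment-emergent summaries promised in SAP 7.2, and the phase-specific versions of the AE tables, most of which are repeated for each study phase and overall. In a descriptive study of about 15 injected participants, with tolerability of a new injection site among its objectives, one participant is a visible part of any incidence.

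**Working it through.** The plan gives no figure on this point to reproduce. The check traces an undated AE through the rules and then sizes the effect.

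**Inputs**
- Missing start date stays missing: SAP 11.6.2.1.
- Rows tested in the order Screen, OLI, Injection, Follow-up: SAP 11.3.1.
- Emergent only if the phase is OLI, Injection or Follow-up: SAP 11.3.2.
- Software SAS 9.4 or higher: SAP 3.2. How missing values are compared is not stated, so both conventions were run.
- About 15 participants injected: Protocol 1.1 and 4.1.

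**Step 1: trace of a missing start date**

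| Convention | Screen row | Later rows | Phase | Emergent? |
|---|---|---|---|---|
| Missing sorts below every date (assumed SAS default) | true | not reached | Screening | no |
| Any comparison with missing is false | false | all false | none | no |

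The two conventions differ on phase but agree on the flag.

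**Step 2: controls.** On an illustrative calendar (OLI start day 1, injection day 40, Week 4 visit day 68), dated AEs behaved as the SAP intends under both conventions:
- day -3 gave Screening, not emergent;
- days 1 and 39 gave OLI, emergent;
- days 40 and 68 gave Injection, emergent;
- day 69 gave Follow-up, emergent.

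The problem is therefore confined to the missing date.

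**Step 3: contrast with partial dates.** Year known and equal to the year of treatment start, day and month unknown, no earlier full stop date: start is set to treatment start, so OLI and emergent. Year also unknown: Screening or no phase, not emergent. The SAP gives no reason for the reversal.

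**Step 4: where the record goes**
- Lost: the treatment-emergent count in Table 3.2, and the OLI, Injection and Follow-up versions of the AE tables.
- Kept: Listing 9 of all AEs.
- Can be kept: the overall AE count in Table 3.2, Table 3.3 (all AEs), and the overall version of the other tables.

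**Step 5: size.** One record belongs to one participant, so the change in an incidence is at most 1/N. With N = 15, 1/15 = 6.7 percentage points, and only if that participant has no other AE counted in the same cell. The cut-off for common AEs is 10%: 2/15 = 13.3% is above it and 1/15 = 6.7% is below. That cut-off is applied to the Total column, so a term crosses it only if the program also drops the unphased event from Total.

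**Step 6: after the change.** With the slotting date set to OLI start, the Screen test (strictly before OLI start) is false and the OLI row is true: OLI, emergent. With an injection site reaction slotted to the injection date, Screen and OLI (strictly before injection) are false and Injection is true: Injection, emergent.

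**The case against.** The strongest reply is that little depends on this in practice.

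- **The trigger may never occur.** Day, month and year must all be missing. AEs are collected at scheduled visits, and monitors verify that CRF entries are complete (Protocol 11.1.6). This stands: the documents give no rate of undated AEs, and in a small Phase 1 study it is probably low.
- **The event does not vanish.** A reader might infer that it drops out of the safety report. The documents do not support that. Overall tables are not restricted to emergent AEs, seriousness and relatedness do not depend on phase, and Listing 9 has a phase column in which a Screening or blank entry would show.
- **Injection site reactions keep their drug.** SAP 7.3 assigns them to CAB or RPV by left or right thigh, not by date, and Tables 3.20 to 3.22 include an overall column. This stands. Only their split between the Injection and Follow-up headers of SAP Table 5 would be affected.
- **The SAP does not contradict the protocol.** Leaving a date missing says nothing about timing. This also stands. The fault is that the phase and flag rules turn an absent date into a non-emergent classification.
- **The error need not always go one way.** For a related SAE recorded between consent and first dose, Screening would be correct. This stands, and any default must allow for it.
- **The Screening outcome depends on unseen code.** True, but Step 1 shows that the flag does not.

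What remains is a stated rule that gives a non-conservative result for the typical AE-form record, with no rationale.

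**Conclusion.** The point holds as a minor one. As written, an AE with a completely missing start date is assigned to Screening or to no phase. It is not treatment-emergent and is absent from every by-phase column, although under Protocol 8.2.1 it is presumptively post-dose.

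The effect is at most one participant per record. The 6.7 percentage points are a ceiling, not an expected effect. They assume a denominator of 15 and no other AE of the same kind in that participant. The Safety population takes in anyone dosed, including those who received only oral drug, so its N may exceed 15 and the change would be smaller. No planned inference is affected, because the study tests no hypothesis. The conclusion assumes that the program follows the phase and flag rules literally; it does not depend on how SAS compares missing values.

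**What to change.** Add to SAP 11.3.2 and 11.6.2.1:

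1. An AE with a completely missing start date is treatment-emergent unless its stop date or another record shows onset before first dose. This leaves pre-dose related SAEs in Screening.
2. For phase slotting only, its start is set to the OLI treatment start date, in line with the existing partial-date rule. Injection site reactions are slotted to the injection date, since they cannot precede it.
3. A non-missing start date (actual or slotting) is required before the Screening test is applied.
4. No study day, time to onset or duration is derived from the slotting date. SAP 11.6.2.1 already says this for imputed partial dates.

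The cost is about two SAP sentences and one program condition. The SAP's revision chronology labels the document as critical components, and Appendix 9 expects a full version to follow, so there is a natural place for the change. The downside is small: some events may be slotted to an earlier phase than the true one, and a footnote giving the number of such records would make that visible.
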